#### Study Arm 2: Community Linkage-To Care Arm (Control Condition) Procedures:

Participants allocated to the community linkage-to-care arm will complete screening, be offered enrollment, and undergo informed consent as in the telemedicine arm. Following study inclusion and enrollment, research staff will refer the participant to a local community health clinic to engage in hepatitis C care and seek treatment. Peers will assist patients to engage with local primary care and health plan resources and will receive an information sheet on optional clinics to attend and questions to ask their provider. TAU participants will be encouraged to take this to their visit. Research assistants will outreach to participants regularly to determine if they have engaged in local health resources and schedule assessment visits. A bidirectional release of information will be requested. The study clinical pharmacist or research assistant will assess adherence medication adherence at week 4 and end of treatment via telephone. SVR12 laboratory testing will be performed by the community provider with at least one telephone reminder prior to lab due date. 12 weeks post end of treatment study assessments will coincide with SVR12 lab results visit and 36 week post end of treatment assessments performed as in the telemedicine arm.

Chart abstraction for participants in both arms will be performed in order to assess the number of and types of interactions the peers have with participants.

In either arm, participants who do not initiate treatment by 12 weeks after randomization will begin their assessment timeline, mirroring treatment timeline for an 8-week direct acting antiviral regimen. For these participants, the study research assistant will collect study assessments at week 16 (corresponding to 4-week post-treatment initiation), week 20-22 (corresponding to end of treatment visit), week 32 (corresponding to 12 weeks post-treatment visit), and week 56 (corresponding to 36

weeks post-treatment visit) after randomization; the primary study outcome will be assessed at 32 weeks after randomization.

Participant Assessments:

Phase 1:

- Blood draw and DBS specimen collection for HCV RNA and Hepatitis B core antibody

Phase 2:

Assessment/Activity	Pre-Screen	Screen	Baseline (Week 0)	4-Week after treatment initiation	End of Treatment	12-week Post-Treatment	***36-Week Post Treatment Completion	As Needed

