## Data Analysis:

Pre-specified analyses for this study will be intention-to-treat (ITT) comparisons between telemedicine and treatment as usual (local treatment referral) on primary and secondary outcomes. Prior to conducting these analyses, we will compare baseline covariate distributions (demographics, etc.) between randomized groups using standardized mean differences (SMDs) and bivariate statistical tests (e.g. t-tests, Chi-square tests). If a significant imbalance in any variable is noted, i.e., a SMD > 0.25 and  $p < .2$ , we will include that variable as a covariate in future analyses. All primary and secondary analyses will utilize generalized linear (mixed) models (GLMMs) with distributions and link functions appropriate for the distribution of the outcome variable. Fixed effects of interest in the models will be timepoint (baseline, 4 weeks, end of treatment, 12 weeks post-treatment, 36 weeks post-treatment), randomized group (telemedicine vs. TAU), and their interaction. If more than one timepoint is included in the analysis, GLMMs will include person-level random intercepts to account for repeated measurements on subjects. Hypotheses will be tested using between-group comparisons at each timepoint of interest, or within-group comparisons across timepoints.

Hypothesis 1: Participants randomized to receive tele-HCV treatment will have superior SVR-12 rates compared to those randomized to TAU (referral for local treatment).

Analytic strategy: We assess the effect of telemedicine versus TAU on SVR at 12 weeks post-treatment completion using logistic regression. Missing HCV viral load data will be considered non-suppressed in the main ITT analysis. Sensitivity analyses will include a per-protocol analysis and a repeat of the main analysis using multiple imputation of missing data.

Hypothesis 2: Participants randomized to receive tele-HCV treatment will have superior rates of HCV treatment initiation (filled first prescription) compared to those randomized to TAU.

Analytic strategy: We assess the effect of telemedicine versus TAU on treatment initiation by 4 weeks post-baseline using logistic regression. Missing treatment initiation data will be considered non-initiated in the main ITT analysis. Sensitivity analyses will include a per-protocol analysis and a repeat of the main analysis using multiple imputation of missing data.

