Hypothesis 3: Participants randomized to receive tele-HCV treatment will have superior rates of HCV treatment completion (filled final prescription and self-reported > 90% HCV treatment pills taken) compared to those randomized to TAU.

Analytic strategy: We assess the effect of telemedicine versus TAU on treatment completion by 12 weeks post-baseline using logistic regression. Missing treatment completion data will be considered incomplete in the main ITT analysis. Sensitivity analyses will include a per-protocol analysis and a repeat of the main analysis using multiple imputation of missing data.

Hypothesis 4: Participants randomized to receive tele-HCV treatment will have a higher likelihood of engagement with harm reduction resources, lower rates of substance use, lower stigma, and higher engagement in addiction treatment resources compared to those randomized to TAU (referral for local treatment).

Analytic strategy: We assess the effect of telemedicine versus TAU on these outcomes at all post-baseline timepoints using mixed effects regression models. Missing outcome data will be handled using full information maximum likelihood. We will conduct per-protocol analyses as sensitivity analyses.

**Qualitative Evaluation.** Audio-recorded interviews will be professionally transcribed; transcripts will be uploaded into qualitative analysis software (NVivo™). Comagine research staff create a coding scheme, conduct coding, and revise in an iterative process that has been successfully implemented by the study team in other mixed-methods projects. The qualitative data provides complementary information to illuminate and expand quantitative findings, including survey results and measures of treatment initiation and completion.

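### Hypothesis 4 compares the arms at visit labels timed from treatment start, so if telemedicine starts treatment more often or sooner, the contrast picks up a bias equal to time slope times mean timing gap

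*Combined protocol and SAP*

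**What the plan says.** The Data Analysis section puts timepoint, randomized group and their interaction in the mixed models and lists the timepoints by label: "Fixed effects of interest in the models will be timepoint (baseline, 4 weeks, end of treatment, 12 weeks post-treatment, 36 weeks post-treatment". The tests follow those labels: "Hypotheses will be tested using between-group comparisons at each timepoint of interest, or within-group comparisons across timepoints". For Hypothesis 4 (harm reduction engagement, substance use, stigma, addiction treatment engagement) it adds: "We assess the effect of telemedicine versus TAU on these outcomes at all post-baseline timepoints using mixed effects regression models".

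The labels are defined elsewhere. The Phase 2 assessment table heads the first post-baseline column "4-Week after treatment initiation", and the later columns count from end of treatment. The Study Arm 2 procedures give the rule for the others, in both arms: "participants who do not initiate treatment by 12 weeks after randomization will begin their assessment timeline, mirroring treatment timeline for an 8-week direct acting antiviral". The survey times for those participants, counted from randomization, are: "week 16 (corresponding to 4-week post-treatment initiation), week 20-22 (corresponding to end of treatment visit), week 32 (corresponding to 12 weeks post-treatment visit"). Their last visit is at week 56.

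The other Hypothesis 4 provisions are a random intercept per participant, full information maximum likelihood for missing outcomes, and a per-protocol sensitivity analysis. None brings in weeks since randomization.

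**The concern.** Whether and when a participant starts treatment is decided after randomization, and the intervention is designed to change it. Hypothesis 2 predicts more initiation with telemedicine, and the Study Arm 1 procedures expect the first telemedicine visit to be the initiation visit for most participants. If that happens, one label refers to an earlier week after randomization in the telemedicine arm than in control.

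The four Hypothesis 4 outcomes can change with time for reasons unrelated to the arm. People recruited through outreach or syringe exchange may regress toward their usual level or move in and out of services. A gap in survey timing turns part of that change into an apparent arm difference, or hides a real one. The random intercept handles correlation within a participant, maximum likelihood handles values that are missing, and the per-protocol analysis changes who is included. None of them aligns the two arms in time.

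**Working it through.** **1. Reproduce the plan's schedule.** With anchor week s after randomization and course length L, visits fall at s+4, s+L, s+L+12 and s+L+36. For non-starters s = 12 and L = 8, which gives 16, 20, 32 and 56. This matches the stated weeks 16, 20-22, 32 and 56.

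**2. Apply the same formula to starters** (most courses are 8 weeks and a small subset 12, per the Study Arm 1 procedures).

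| Participant | '4 weeks' | End of treatment | 12 weeks post | 36 weeks post |
|---|---|---|---|---|
| Start week 0, 8-week course | 4 | 8 | 20 | 44 |
| Start week 4, 8-week course | 8 | 12 | 24 | 48 |
| Start week 0, 12-week course | 4 | 12 | 24 | 48 |
| Not started by week 12 | 16 | 20-22 | 32 | 56 |

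Between an immediate starter on 8 weeks and a non-starter, each label differs by about 12 weeks.

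**3. Mean gap between arms.** The documents give no start rates, so assume that 80% of telemedicine start at week 4, 30% of control start at week 8, and the rest do not start. The mean week of the '4-week' visit is:

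- telemedicine: 0.8 × 8 + 0.2 × 16 = 9.6
- control: 0.3 × 12 + 0.7 × 16 = 14.8
- gap: 14.8 − 9.6 = 5.2 weeks

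**4. Bias.** With no true arm effect and a linear trend of b per week, the expected difference (telemedicine minus control) is b × (9.6 − 14.8) = −5.2b. For an assumed |b| of 0.5 to 1 percentage point per week, its size is 2.6 to 5.2 points. If substance use is falling, telemedicine looks worse because it is surveyed sooner. If it is rising, telemedicine looks better.

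**5. Sensitivity to the assumptions.** Mean anchor week = p × start week + (1 − p) × 12, where p is the proportion starting. The false-positive rate is for a two-sided test at 0.05 with 100 per arm. Both are assumed: the plan says up to 200 participants and gives no allocation ratio, and it gives no alpha for this hypothesis. The standard error is √(2/100) = 0.141 SD.

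| Telemedicine vs control (assumed) | Mean anchor week | Gap | 0.01 SD/week | 0.02 SD/week | 0.04 SD/week |
|---|---|---|---|---|---|
| 70% at wk 4 vs 50% at wk 6 | 6.4 vs 9.0 | 2.6 | 0.03 SD, 5.4% | 0.05 SD, 6.6% | 0.10 SD, 11.4% |
| 80% at wk 3 vs 40% at wk 6 | 4.8 vs 9.6 | 4.8 | 0.05 SD, 6.3% | 0.10 SD, 10.4% | 0.19 SD, 27.4% |
| 85% at wk 2 vs 20% at wk 8 | 3.5 vs 11.2 | 7.7 | 0.08 SD, 8.5% | 0.15 SD, 19.3% | 0.31 SD, 58.6% |

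Simulation (4,000 runs) of the last two rows gave 10.3% and 19.1% at 0.02 SD/week, and 27.7% and 57.4% at 0.04. With the same start-time distribution in both arms, the rate was 4.8% to 5.4% at every slope tried.

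**6. Does a change of time axis help?** A further null simulation used a mean gap of about 5 weeks, a drift of 0.02 SD/week and 100 per arm. The visit-label contrasts showed a false difference of about 0.10 SD and 11-13% rejection. A spline in weeks since randomization by arm, with a random intercept, cut the bias to at most about 0.03 SD and rejection to about 4-7%, even when starting treatment depended on the participant's own level.

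**The case against.** **Stage-of-care alignment is deliberate.** The plan chooses to mirror the treatment timeline, and comparing people at the same point of their care is a legitimate question. That stands as a reason to keep the visit-label model. It does not make that model a comparison at equal time since randomization.

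**The inputs are assumed.** No start rate or trend is in the documents. The larger drifts are hard to sustain: 0.5-1 point per week over 56 weeks is 28-56 points, and 0.02-0.04 SD per week is about 1.1-2.2 SD. A real trend is more likely to be front-loaded, as regression to the mean usually is, and the bias would then sit mainly at the early visits. This stands, and the figures are illustrations only.

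**Re-timing cannot rescue every week.** Participants who start at week 0 or 4 on an 8-week course are last seen at week 44 or 48, so a week-56 contrast would rest on non-starters and extrapolation. Starters at week 4 have no visit between weeks 24 and 48, and the 36-week survey goes only to those who qualify. This stands against week 56. At weeks 16 and 32 the model interpolates within the observed range, and the simulation in step 6 suggests this is adequate.

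**Stronger readings.** A reader might infer that any time trend passes in full into the arm effect. It does not: only slope times mean gap does, and that is zero if start times do not differ by arm. A reader might also infer that visits under one label can spread much further because the Study Measures section counts treatment starts up to 6 months. The documents do not settle which anchor applies to someone who starts between week 12 and 6 months, so no upper limit can be drawn from that group. The two sections must be reconciled.

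**Conclusion.** The point holds for Hypothesis 4. The plan compares arms at labels whose week after randomization depends on a post-randomization event that the intervention targets, and no planned analysis corrects for it. The bias is the time slope multiplied by the between-arm gap in mean survey week. It can favour or penalize telemedicine, and its size cannot be fixed from the documents. The worked example gives 2.6-5.2 percentage points. Across the assumed scenarios the false-positive rate runs from little above 5% (5.4%) to well above it, and the highest values need a steep trend sustained throughout follow-up.

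The scope is limited. The baseline visit is week 0 in both arms. Hypotheses 2 and 3 use windows counted from baseline. Anchoring to treatment is natural for SVR12, and nothing here bears on the primary analysis. Because four secondary outcomes are affected and the remedy is cheap, the change is worth making before the analysis.

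**What to change.** For Hypothesis 4, fit the mixed model with actual weeks since randomization as a low-degree-of-freedom smooth (for example a spline) by arm, with a random intercept per participant. Use the date each survey was administered. This assumes that date is captured in REDCap; since surveys may be completed on paper and entered later, the entry date will not serve.

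Take the between-arm contrasts at common weeks inside the observed range of both arms, such as weeks 16 and 32, and name them in advance. Do not use week 56 as a main contrast. Report the visit-label model alongside, described as a stage-of-care comparison that is not aligned on time since randomization, and tabulate survey week by label and arm so that the gap is visible. Separately, reconcile the 12-week rule in the Study Arm 2 procedures with the 6-month rule in Study Measures, so that the visit anchor for late starters is defined.

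The cost is SAP wording and a few model degrees of freedom, with no new visits. The price is some interpolation between visits, slightly wider intervals at some weeks, and a small residual bias if the week of observation is related to who starts treatment.

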### Study Arm 1: Tele-HCV Treatment Arm Procedures:

Participants allocated to telemedicine intervention arm are scheduled for treatment assessment by a study clinician. For a majority of participants, this will also be the treatment initiation visit. If additional studies are necessary for routine treatment decision making, peers will assist participants in navigating health system barriers and arrangement of second telemedicine visit. The telemedicine study clinician will perform a standard of care hepatitis C treatment initiation history and submit a prescription for DAAs. Prior authorizations will be completed by study clinician pharmacist.

All patients initiating treatment will be prescribed HCV medication treatment for 4 weeks at a time. The majority of patients will require two separate dispensations at week 0 and week 4 for a total of 8 weeks of medications, with a small subset requiring third, 4-week dispensation for a total of 12 weeks of therapy. The study clinical pharmacist will check in with the participant by telephone or telemedicine visit at week 0, week 4, and end of treatment to 1) determine general medication tolerance, 2) assess quality of adherence and 3) dispense medications by mail or ensure medications received, depending on participant's insurance. Peers will assist participants in keeping telehealth appointments and navigating medication pick up or storage, if not mailed directly to the home. Participants who report new onset of jaundice or other signs of hepatic decompensation during participation will be scheduled for a follow up telemedicine visit with a physician by the research assistant, receive repeat laboratory studies if needed, and if necessary, be referred to local providers for ongoing medical care. If problems or side effects arise during treatment, participants will call the research assistant, who will connect them to a study clinician.

HCV labs will be repeated at 12 weeks post end of treatment and results will be relayed to the participant in the SVR12 follow up visit with the research assistant, along with follow up surveys. Those successfully achieving SVR12 will be counseled on ongoing harm reduction methods. Those showing persistent HCV viremia at 12 weeks post treatment will be referred to community-based HCV treatment providers for treatment re-initiation. All will be scheduled for 36 week post end of treatment survey visit.

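### For continuous Hypothesis 4 outcomes, a random intercept as the only within-person structure mis-sizes the long-gap within-group tests and can mis-size the 36-week arm comparison

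*Combined protocol and SAP*

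**What the plan says.** The general paragraph of the Data Analysis section sets up generalized linear mixed models "with distributions and link functions appropriate for the distribution of the outcome variable". The fixed effects are "timepoint (baseline, 4 weeks, end of treatment, 12 weeks post-treatment, 36 weeks post-treatment), randomized group (telemedicine vs. TAU), and their interaction". On within-person dependence it says only: "If more than one timepoint is included in the analysis, GLMMs will include person-level random intercepts to account for repeated measurements on subjects". No random slope, residual covariance structure, visit-specific variance or robust standard error is mentioned anywhere.

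On testing, the same paragraph says: "Hypotheses will be tested using between-group comparisons at each timepoint of interest, or within-group comparisons across timepoints".

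The Hypothesis 4 strategy estimates the arm effect "on these outcomes at all post-baseline timepoints using mixed effects regression models" and adds: "Missing outcome data will be handled using full information maximum likelihood". Its only sensitivity analysis is per-protocol.

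The visits are unevenly spaced. The Study Arm 1 procedures say most participants need "two separate dispensations at week 0 and week 4 for a total of 8 weeks of medications". Counted from treatment start, that puts visits at weeks 0, 4, 8, 8 + 12 = 20 and 8 + 36 = 44. The Study Arm 2 procedures place the corresponding visits of non-initiators in either arm at weeks 16, 20 to 22, 32 and 56 after randomization. A footnote to the assessment table makes the 36-week survey conditional on the participant qualifying.

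**The concern.** For a normally distributed outcome, a random intercept with independent residuals is compound symmetry: one variance at all visits and one correlation for every pair. Scores taken 4 weeks apart would be expected to agree more closely than scores taken 44 weeks apart. If so, the fitted common correlation is too high for long gaps and too low for short ones. The standard error of a long-gap change is then too small.

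The covariance also matters for missing data. Full information maximum likelihood recovers a missing late score through its assumed correlation with earlier scores. If that correlation is overstated, early visits get too much weight, and the missing-at-random assumption is not enough to protect the result. At stake are the false-positive rate and, in some dropout patterns, the bias of secondary comparisons at the longest follow-up.

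**Working it through.** The documents give no SD, correlation, dropout rate or power figure for Hypothesis 4, so there is no figure of the plan's own to reproduce.

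**Assumptions (not in the documents).** Normal outcome; two-sided 5% test; visits at weeks 0, 4, 8, 20 and 44; saturated arm-by-visit means; correlation 0.8 × exp(−gap/40).

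**Method.** Fit compound symmetry to the assumed true covariance by maximum likelihood. Let k be the model-based SE divided by the true SE. Actual type I error = 2Φ(−1.96k).

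**Step 1: common correlation, complete data, constant SD.** The ten pairwise correlations are 0.724, 0.655, 0.485, 0.266, 0.724, 0.536, 0.294, 0.593, 0.325 and 0.439. Their mean is 5.042/10 = 0.504, which is what the random-intercept model fits.

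**Step 2: within-group change.** With constant SD, k = √[(1 − 0.504)/(1 − true correlation)].
- Baseline to week 44: √(0.496/0.734) = 0.822; error 2Φ(−1.61) = 0.107.
- Baseline to week 4: √(0.496/0.276) = 1.34; error 2Φ(−2.63) = 0.009, so short-gap comparisons are conservative.
- If only the four post-baseline visits are modelled, the mean correlation is 2.912/6 = 0.485. For week 4 to week 44, k = √(0.515/0.706) = 0.854 and the error is 0.094. The problem does not depend on baseline being in the outcome vector.

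A between-arm difference in change has the same k.

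**Step 3: between-arm test at one visit, complete data.** The SE depends only on the variance at that visit, so k = fitted SD / true SD. With constant SD, k = 1.000 and the error is 0.050, whatever the correlations. With SD rising evenly by visit from 0.9 to 1.25, the fitted variance is the mean of the five squared SDs, 5.855/5 = 1.171. At week 44, k = √(1.171/1.5625) = 0.866 and the error is 0.090. With the SD reversed, k = √(1.171/0.81) = 1.202 and the error is 0.018.

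**Step 4: dropout.** Retention 100/90/85/75/64%, completely at random.

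| Scenario | Arm test, week 44 | Within-group, 0 to 44 |
|---|---|---|
| Constant SD, complete | 0.050 | 0.107 |
| Constant SD, dropout | 0.068 | 0.119 |
| Rising SD, complete | 0.090 | 0.105 |
| Rising SD, dropout | 0.114 | 0.131 |
| Falling SD, complete | 0.018 | 0.116 |
| Falling SD, dropout | 0.030 | 0.113 |

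The arm test at week 20 (12 weeks post-treatment) has error 0.051 with constant SD and dropout. With complete data and rising SD, k = √(1.171/1.351) = 0.931 and the error is 0.068.

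**Step 5: other correlation shapes.** Other decaying patterns were tried, with 0.7 to 0.95 at 4 weeks and 0.20 to 0.57 at 44 weeks, complete data and equal variance. The arm test at week 44 stayed at 0.050. The baseline-to-week-44 change ranged from 0.109 to 0.160.

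**Step 6: dropout that depends on the score.** Two simulations used 100 per arm, no true effect, constant SD, and dropout tied to the last observed score in controls only. Under the random-intercept model the week-44 arm contrast was biased by 0.09 and 0.10 SD, with rejection rates of 10.3% (1,200 runs) and 11.9% (1,000 runs). The first simulation also fitted an unstructured covariance, which rejected 4.4 to 6.6% over its six scenarios (Monte Carlo SE 0.6 to 1.0 points).

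**The case against.** Several points on the other side stand.

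- A reader might infer that uneven spacing alone gives the late between-arm tests wrong standard errors. It does not. With complete data and constant variance the week-44 arm test is exactly sized. It needs missing late data or changing variance to go wrong, and with falling variance it errs on the conservative side. The 12-week comparison is little affected unless the variance changes.
- A reader might extend the point to every Hypothesis 4 outcome. The plan chooses distribution and link by outcome, and engagement and substance use may well be binary or counts, for which equal variance is not implied. Simulated binary outcomes with serial correlation gave 0.040 to 0.060 for the last-visit arm test, against 0.047 to 0.048 when the model was correct. For the change contrast they gave 0.045 to 0.068 against 0.058 to 0.065. With a Monte Carlo SE of about 0.009, no distortion is shown, so there is no case here for changing the binary models.
- Hypothesis 4 is itself a between-arm claim, and the clearest error is in within-group comparisons. The general paragraph nonetheless lists those as a way of testing hypotheses.
- The text says the models will include random intercepts, not that nothing else may be added. But nothing else is specified.
- The larger figures for the arm test depend on SD and dropout patterns for which the documents give no evidence. The conditional 36-week survey does make incomplete last-visit data likely.
- The remedy was not tested with initiators and non-initiators on different schedules, and Kenward-Roger degrees of freedom were not simulated.

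**Conclusion.** The point holds for Hypothesis 4 outcomes analysed as continuous, of which stigma is the plausible example. Under the assumed decaying correlation, the within-group comparison from baseline to the 36-week visit has a type I error of 0.105 to 0.131 in every scenario tried, including complete data with constant SD (0.107). The between-arm test at that visit is sound in the simplest case. It can be miscalibrated in either direction (0.018 to 0.114 in the scenarios above), and it can be biased by about 0.1 SD when dropout depends on earlier scores and differs by arm.

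All sizes rest on assumed correlations, SDs and retention. The affected outcomes are secondary. Hypotheses 1 to 3, including SVR12, use logistic regression on a single outcome per person and are untouched. This is a cheap improvement to the SAP and not a threat to the trial's main conclusion.

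**What to change.** In the Data Analysis section, for Hypothesis 4 outcomes analysed as continuous, replace the person-level random intercept with an unstructured within-person covariance over the five visits (5 × 6/2 = 15 parameters), with Kenward-Roger degrees of freedom. Name a fallback in advance, such as heterogeneous Toeplitz, for use if the model does not converge. State which outcomes will be analysed as continuous. Leave the binary-outcome models and Hypotheses 1 to 3 as they are.

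The cost is SAP wording and a different model option, with no new data. The downsides are a small risk of non-convergence, hence the fallback, and sometimes slightly wider intervals.

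### The general testing rule admits within-arm change as a hypothesis test; this conflicts with the between-arm hypotheses and leaves Hypothesis 4, though not SVR12, without a named deciding contrast

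*Combined protocol and SAP*

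**What the plan says.** The Data Analysis section opens with a between-arm commitment: "Pre-specified analyses for this study will be intention-to-treat (ITT) comparisons between telemedicine and treatment as usual (local treatment referral) on primary and secondary outcomes". It then describes generalized linear (mixed) models with fixed effects for timepoint (baseline included), "randomized group (telemedicine vs. TAU), and their interaction", and closes that general paragraph with the testing rule: "Hypotheses will be tested using between-group comparisons at each timepoint of interest, or within-group comparisons across timepoints". The rule is not limited to particular hypotheses, and within-group results are not called descriptive.

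Each hypothesis is worded as telemedicine against TAU and has its own strategy. For Hypothesis 1: "We assess the effect of telemedicine versus TAU on SVR at 12 weeks post-treatment completion using logistic regression". For Hypothesis 2: "We assess the effect of telemedicine versus TAU on treatment initiation by 4 weeks post-baseline using logistic regression". Hypothesis 3 has the same form, for treatment completion. For Hypothesis 4: "We assess the effect of telemedicine versus TAU on these outcomes at all post-baseline timepoints using mixed effects regression models". That last strategy names the between-arm effect, but it does not say which timepoint, contrast or interaction test decides the hypothesis.

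The assessment table under Participant Assessments schedules the Hypothesis 4 domains at baseline and at up to four later visits; the 36-week survey is only for participants who qualify.

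**The concern.** A within-arm change mixes any effect of the arm with everything else that happens after enrolment. Here a change common to both arms is plausible. Phase 2 entry requires injection or recreational opioid use in the last 90 days and that the person is seeking HCV treatment, so some movement back from a recent extreme can be expected. The control arm also receives peer help to engage with local care. If within-arm change is accepted as a test, improvement shared by both arms could be reported as support for telemedicine. The same error arises when significance in one arm is set against non-significance in the other.

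A second, smaller matter is precision. The between-group comparison at each timepoint, taken from a model in which baseline is one more timepoint, does not in general adjust for the baseline value of the outcome, although that value is collected.

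**Working it through.** **Is there a figure to reproduce?** No. For Phase 2 the documents give no power, effect size, SD, alpha, dropout or allocation ratio. The following is illustration under stated assumptions.

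**Inputs**
- n = 100 per arm. Number of Subjects gives up to 200; equal allocation and no dropout are assumed.
- Two-sided 0.05 (critical value 1.96), continuous outcome with SD 1 (assumed).
- Within-person correlation r = 0.5, with range 0.3 to 0.7 (assumed).
- The same true improvement d in both arms and no arm effect (assumed).

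**Test within the telemedicine arm**
- SE of mean change = sqrt(2(1 − r)/n) = sqrt(2 × 0.5/100) = 0.10.
- d = 0.2: z = 2.0, and P(significant, favourable) = Φ(2.0 − 1.96) = 0.516.
- d = 0.3: z = 3.0, and P = Φ(3.0 − 1.96) = 0.851.
- Over r = 0.3 to 0.7: 0.39 to 0.73 at d = 0.2, and 0.72 to 0.97 at d = 0.3. With no shared change it is 0.025.

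**Significant in telemedicine, not in TAU**
- The arms are independent, so the probability is p(1 − p).
- d = 0.2: 0.516 × 0.484 = 0.25. d = 0.3: 0.851 × 0.149 = 0.13.
- Doubling these gives 0.50 and 0.25 for exactly one arm significant, but half of those cases favour TAU.

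**Between-arm test**
- In 20,000 simulated trials per setting, the follow-up difference and the group-by-time contrast each favoured telemedicine in 0.022 to 0.027 of trials, whatever the shared change.
- If either a between-arm or a within-telemedicine result counts, as a literal reading of the rule allows, the rate at r = 0.5 is 0.51 (d = 0.2) or 0.84 (d = 0.3).

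**Binary example (normal approximation, r = 0.3 to 0.5)**
- Substance use falling from 70% to 60% in both arms: the within-telemedicine test is significant with probability 0.43 to 0.56.
- Falling from 70% to 50%: 0.94 to 0.99.

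**Baseline adjustment, continuous outcome, complete data**
- A group-by-timepoint model with unconstrained baseline means returns the raw follow-up difference, with variance 2/n = 0.020.
- Adjusted for baseline, the variance is 2(1 − r²)/n. At r = 0.5 this is 0.015, a 25% reduction; at r = 0.7 it is 0.0102, a 49% reduction.

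**The case against.** The strongest reply is that the specific text governs the general. The section opens with between-arm ITT comparisons, all four strategies assess telemedicine against TAU, and no hypothesis is assigned a within-group test. This stands, and for Hypotheses 1 to 3 it is decisive. They are logistic regressions at one timepoint, and participants enter RNA-positive and untreated, so a contrast with baseline has no useful meaning. A reader might infer from the general rule that the SVR12 conclusion could rest on within-arm change; the documents do not support that.

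For Hypothesis 4 the reply is weaker. Its strategy points to a between-arm effect but leaves the deciding contrast open, and the only sentence that says how hypotheses are tested from the repeated-measures model is the permissive one.

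It is also fair that the 52% to 85% is not an error rate of the Hypothesis 4 analysis as described. It applies only if the within-group option is used, and the shared change and the correlation are assumptions.

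On baseline adjustment, an unadjusted contrast in a randomized trial is valid. Baseline values are not ignored altogether either: they enter the mixed model as outcomes and inform the estimates when follow-up is missing. The imbalance rule (SMD above 0.25 and p below 0.2) might bring in baseline variables, but it does not assure adjustment for the baseline outcome. The r² gain applies to continuous outcomes with complete data. Several Hypothesis 4 outcomes may be binary, and there the gain differs.

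**Conclusion.** The point holds as a conflict of wording whose practical reach is Hypothesis 4. The within-group clause is unrestricted and cannot test any of the stated hypotheses. Where outcomes are repeated and no deciding contrast is named, it leaves room for a false claim. Under the stated assumptions, that claim would arise 52% to 85% of the time from a test within telemedicine alone, and about 13% to 25% of the time from contrasting significance between arms. The between-arm rate is about 2.5%.

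Two stronger readings should be set aside. A reader might infer that the plan intends to decide its hypotheses by within-arm change; the opening commitment and the four strategies say otherwise. A reader might also take the 25% to 50% chance that exactly one arm is significant as the rate of false support for telemedicine; that figure counts both directions. The lack of assured baseline adjustment for Hypothesis 4 is a loss of precision and not a source of bias.

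**What to change.** 1. In the general paragraph of Data Analysis, delete the within-group option as a hypothesis test, or state that within-arm changes are descriptive and support no claim about telemedicine.
2. In the Hypothesis 4 strategy, name the between-arm contrast at the post-baseline timepoints as the test, and state which timepoint or timepoints decide each outcome.
3. Adjust that contrast for the baseline value of the outcome, either as a covariate or by constraining the arm means to be equal at baseline in the mixed model, irrespective of the imbalance rule.

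The cost is a sentence or two in the plan and a standard model option. No new data are needed, because the baseline surveys are already scheduled.
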